**Biomechanical Testing (all testing sessions):**

Equipment:

C-MOVA: 1. NEW Qualisys MoCap system, markers and straps (NO EMG/ACCELEROMETERS)

Methods:

**BEGINNING KINEMATIC SAMPLE RATE = 120 Hz**

1. Standing Calibration (named sc)
2. Self-selected walking speed (3, 6 months)
  - a. 8 trials collected on each limb (named walk01, etc.)
3. Bilateral squats (eyes open, arms folded across chest, re-do trial if balance is lost) (2 weeks & 3, 6 months)
  - a. 1 trial = 5 squats
  - b. 1 practice, 3 collected trials of max squats (named bilsquatmax01, etc.)
  - c. **Metronome: 3 seconds down, 3 seconds up**
    - i. **Verbal cues: “Down, 2, 3, Up, 2, 3”**
  - d. Pain is only to increase by 2/10 from pain in standing; either 1) modify depth of squats or foot position or 2) omit the testing (if unable to test involved max squats, still completed unininvolved max squats)

**Surveys (all testing sessions):**

1. Complete on laptop/tablet using REDCap

### **Infectious Disease Control**

1. Participants and study personnel will wash hands or use hand sanitizer before beginning testing session.
2. All equipment will be disinfected after participant use/testing including wraps, mat table, and Biodex.
3. Actigraph accelerometers (per return in mail) will be disinfected and strap will be washed before next use.
4. During COVID-19 period, research participants will be screened using the procedures outlined in “General\_Travel\_Screen\_Research”. Any participants screening positive will have testing session re-scheduled or cancelled as needed according to current UNMC procedures.

## Biomechanics Data Collection

### Equipment:

1. 29 markers (no anterior thigh or tibial tuberosity)
2. non-reflective tape
3. athletic tape
4. Coban
5. Velcro small straps for shorts
6. White wraps for thigh and shank
7. NO EMG/Accelerometers

### Methods:

#### 4. Camera Set-Up

- a. Place markers to define desired data collection volume
- b. Check each camera to optimize the amount of volume seen by each camera (i.e. move cameras if necessary)

#### 5. Frequency Settings

- a. Tools → project options → Camera Frequency 120 Hz ; Analog boards 1080 Hz

#### 6. Camera Exposure Settings

- a. Using Intensity mode (intensity button on right sidebar) adjust the exposure and marker threshold so that markers are red and there is no extra blue markings in the background. It is best to have a high exposure and a low marker threshold.
- b. Repeat this with all 8 cameras
- c. Default Threshold = 17
- d. No Exposure Default

#### 7. Qualisys Calibration (This should be done before subject enters room)

- a. Select correct project when opening Qualisys (Miqus 8 camera Marker Only)
- b. Before beginning, make sure all reflective markers are out of sight and zero all 3 force plates
- c. Find Calibration tools under desk in black toolbox and assemble T wand and Right angle
- d. Place Right Angle piece on Right Top (northwest) Force plate (when looking out from desk) in exactly the right corner
- e. In upper L. corner in Qualisys, hit "New"
- f. Check to see that all cameras are working by looking for a "4" in the right bottom corner of each screen
- g. Hit "Calibrate" Tool
- h. Set parameters: 60 seconds to calibrate, 5 second delay → ok
- i. Wave T wand at low, medium, and high heights for 1 minute
- j. At end of calibration, all cameras should be less than .4 (look at far right column)
- k. Create Folder in temporary desktop location for subject using identification code: (Squat01001, Squat02002, etc...)

1. Set folder path in Qualisys: Click “Record --> Browse” and select the subject’s folder created in step J

**8. Application of reflective markers (29 total)**

- a. \*\*See “Marker Set.doc”
- b. medial metatarsal head, lateral metatarsal head
- c. medial malleolus, lateral malleolus (center of malleoli)
- d. two on posterior heel on shoe (1 superior and one inferior in a line)
  - i. on rigid part of shoe, not too close to ground (do not want inferior marker to hit ground when walking)
- e. Medial Femoral epicondyle most prominent part (small squat can get soft tissue out of the way)
- f. Lateral Femoral Epicondyle (find fibular head and joint line, most prominent part superior to joint line, small squat can move soft tissue out of the way)
  - i. \*\*Medial Epicondyle is usually lower than lateral epicondyle
- g. ASIS
- h. Most superior point of iliac crest in line with greater trochanter
- i. PSIS
- j. Acromion (midpoint of tip)
- k. C7 and sternum
- l. Upper Back (left and right; inferior and toward spine so not affected by scapular movement)
- m. T10

**9. Application of Shells:**

- a. Foot: lateral met head, and two markers on posterior heel make up tracking marker, place extra tape on these to secure into place
- b. Shank:
  - i. Place a wrap around each shank
  - ii. Place smaller rectangle shell on lateral shank
  - iii. Secure shell with athletic tape
- c. Thigh:
  - i. Place a wrap around each upper ½ of thigh
  - ii. Place larger rectangular shell on lateral aspect of thigh
  - iii. Secure shell with athletic tape
- d. \*\*Cover up any reflective material on shoe or clothing with non-reflective tape

**10. Data Collection**

- a. **Qualisys (TO BEGIN: cameras 120 Hz, Force plates 1080 Hz)**
  - i. Tools -> project options -> camera system under input devices. Ensure cameras are set to 120 Hz and Force plates are set to 1080 Hz
  - ii. Zero out each force plate by hitting the red button on each of the black boxes on the right side of the desk
  - iii. Double check to make sure that all reflective materials are out of sight
  - iv. Check that standing calibration model is active

1. Tools > Project Options > AIM > Select correct model (change to movement model after the standing calibration)
- v. Hit "New" → 3D
  1. Use middle button on mouse to zoom in and out
  2. Left mouse button=rotation
- vi. Hit "Record" when ready to collect and select subject folder ("[name]") → Data
- vii. Set amount of time to record data and name trial (all lowercase)
  1. Standing calibration: 1 sec (**sc**)
  2. Walk trials: 5 sec (**walk01, etc.**)
  3. Bilateral squats: 30 sec, (**bilsquatmax01, etc.**)
- viii. Press Start
- ix. Tell patient to "go"
- x. If trial ends before time runs out, can manually press "stop" or press the trigger
- xi. Click qtm file to review trial
- xii. If poor data, can override after pressing "new" by moving counter back to previous trial

## Bodyweight Squat Protocol

### **Eligibility:**

Inclusion: ACLR within 6 months of ACL injury, 13-35 years old

Exclusion: reconstruction,

concomitant cartilage procedures, previous knee injury or surgery to either knee, BMI>35 kg/m^2, current or planned pregnancy during study period

### **Timing:**

Initiation: 2 weeks post-ACLR

Expected # of visits: 16

Frequency of visits: 2x/week

Expected Duration: 10 min/visit

### **Bodyweight Squat Protocol**

Time after ACLR	Sessions	Sets and Reps	Visual Biofeedback Group	Control Group
Weeks 3-4	1,2,3,4	6 sets, 5 reps	GRF only	No visual feedback
Weeks 5-6	5,6,7,8	5 sets, 8 reps	COP only	No visual feedback
Week 7	9,10	6 sets, 8 reps	GRF, COP or None	No visual feedback
Weeks 8-9	11,12,13,14	5 sets, 10 reps	GRF+COP combined	No visual feedback
Week 10	15,16	6 sets, 10 reps	GRF, COP, GRF+COP or None	No visual feedback

### **Protocol Details (for both groups):**

**Timing of Squat Protocol:** Randomly varied by PT during each visit (either before or after strengthening exercises)

**Location of Squat Protocol:** Randomly varied by PT during each visit (either in isolated quiet room or shared exercise space with others)

**Verbal Instructions For Control Group (completed on force plates; no mirror or any visual feedback):**

1. Complete squats keeping knees in line with toes
2. Keep hips back
3. Keep your weight evenly balanced between your feet

**Rest Breaks:** At least 30 seconds between each set

**Squat Depth:** 0-90° (as able)

**Arm Position:** Randomly varied by PT during each set (crossed over chest, straight out, or at side)

### **Progression Plan**

- If participant doesn't miss any appointments progress through the weeks as outlined above
- If participant misses any appointments
  - o If participant has not performed at least 75% of the sessions at a specific level (ex - week 1-2 are a single level) then continue within that same level
  - o If participant has performed at least 75% of session at a specific level then progress to next level
  - o For levels where there are only 2 sessions, participants who perform at least 1 of the 2 sessions can be progressed to the next level
- If individual misses over 75% of all sessions then they may not be included in final analysis, but will remain in the study

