**Recruitment & Patient Tracking**

-[name] Team will keep a potential patient tracking spreadsheet on Box to track pre-op and early post-operative eligible patients

-Potential participants will be discussed at bi-weekly meetings

-When patient is ready to enroll:

1. [name] will email consent form and study info to patient/parents
2. [name] will assign subject ID, enter into REDCap, complete REDCap screening form, and assign to group (post-ACLR)
3. If pre-intervention PT is needed, [name] will schedule first treatment session
4. [name] will inform RJ of when patient is to be in clinic for RJ to meet patient and schedule testing sessions.

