  - Verbal Instructions: "This will be a combination of the two versions you've previously done. Your goal is to keep the green/blue bar as close to the vertical line in the middle of the screen as possible and to keep the green/blue line level and even with the dotted line in the middle of the screen. As you shift to the left the bar will shift left with you and eventually turn red. As you shift to the right the bar will shift right with you and eventually turn red. If the bar isn't visible, it means your weight is evenly distributed side to side. Now, if you put weight through your left heel and right toe the line will tilt and eventually turn red. If you put weight through your right heel and left toe the line will also tilt and eventually turn red. Your goals are to keep both the bar and the line green/blue. You will be performing \_\_\_\_ squats with your arms \_\_\_\_\_. I will give you a countdown to begin your squats. The countdown will be '3,2,1,Go' and we want you to begin on 'Go.' Again the goal is to keep the green/blue bar as close to the vertical line in the

middle of the screen as possible and the green/blue line as level as possible and even with the dotted line in the middle of the screen.”

- Control Cues
  - “I’d like you to squat with your arms \_\_\_\_, keeping your knees in line with your toes, hips back, and weight evenly balanced between your feet. I will give you a countdown to begin your squats. The countdown will be ‘3,2,1,Go’ and we want you to begin on ‘Go.’”

Bodyweight Squat Protocol Modifications	
Factor	Rehab Modification
>50% weightbearing restriction (e.g. due to complex concomitant meniscal repair)	
 
Complete baseline study testing and initiate bodyweight squat protocol when 50% weightbearing is allowed (e.g. at 4 weeks or 6 weeks after ACLR)
 
Full 8 weeks of squat protocol is still completed
 
Delay post-intervention testing (e.g. if squat protocol is initiated at 4 weeks post-ACLR, complete post-intervention testing at 12 weeks post-ACLR instead of 10 weeks post-ACLR)
 

<90° knee flexion ROM restrictions	
 
Complete squat protocol within ROM restrictions (e.g. only squat to 60° until greater knee flexion ROM allowed)
 

< 16 visits completed within squat protocol	
 
Include participant data if at least 8/16 visits are completed during the 8 week squat protocol
 

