## Statistical Analysis Plan

### **Data analysis plan:**

A p-value less than 0.05 will be considered statistically significant unless otherwise specified.

To determine the efficacy of the visual biofeedback program, analyses of covariance (ANCOVA) will be used at 3 and 6 months after ACLR to test differences in the interlimb ratio (ILR = injured limb / uninjured limb) of the knee flexion moment impulse during squatting, after adjusting for baseline knee flexion moment impulse. An ANCOVA will also be used to test differences in the ILR of the vertical ground reaction force impulse.

Independent t-tests will be used to test the percent change in cartilage T2 relaxation time in the injured knee from 2 weeks to 6 months after ACLR between groups, quadriceps strength, and gait biomechanics. For quadriceps strength, limb symmetry indexes will be computed (LSI = injured limb / uninjured limb x 100%).

If assumptions for any of these tests are violated, a nonparametric test will be conducted.

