### **Sample size analysis:**

Using our preliminary data, a sample size of 20 (10 per group) achieves 82.5% power to detect a difference in the knee flexion moment (KFM) impulse ILR of 0.283 during squats between the biofeedback (expected ILR=0.800±0.183) and standard of care group ( expected ILR=0.517±0.228) using a two-sided hypothesis test and p-value of 0.05. Group differences are based on our preliminary data after standard of care: KFM impulse ILR at 4 months (N=20): 0.517±0.228; KFM impulse ILR at 10 months (N=5): 0.971±0.183. Thus, our expected KFM impulse ILR for the biofeedback group at 3 and 6 months is 0.800±0.183. To test our hypothesis that the biofeedback group will walk with a greater KFM than the standard of care group, the minimal detectable change (MDC) of 0.09 N·m/kg·m with a standard deviation of 0.08 was used (Gardinier 2013). Using this expected group difference, a sample size of 28 (14 per group) achieves 81.7% power using a two-sized hypothesis test and p-value of 0.05. To account for 10% attrition, 32 participants will be enrolled.

A sample size of 30 (15 per group) achieves 81.0% power to detect a group difference of  $2.9 \pm 2.7$  milliseconds in T2 relaxation time (primary outcome; measured from 2 weeks to 6 months in the injured knee). This expected group difference is based on a change in T2 relaxation time of  $2.9 \pm 2.7$  milliseconds in the medial femoral cartilage by 6 months after ACLR as reported by Kumar et al. Preliminary data of 37 participants from our ongoing NIH R21 study indicate that quadriceps strength LSI following standard care is  $66.0 \pm 21.1\%$  at 6 months after ACLR. The evidence-based clinical targets for quadriceps strength at 6 months is 90.0%. Using the expected quadriceps strength LSI of 66.0% in the control group and 90.0% in the intervention group at 6 months after ACLR with a pooled standard deviation of 21.1%, a sample size of 30 (15 per group) achieves 91.8% power using a two-sided hypothesis. To account for attrition, 34 participants will be enrolled.

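### Two attendance rules leave participants with 4 to 7 of 16 sessions unsettled, no analysis set decides the matter, and both rules select on attendance after group assignment

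*Combined protocol and SAP*

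**What the plan says.** The Timing section of the Bodyweight Squat Protocol plans a fixed number of sessions ("Expected # of visits: 16"). Two places then say what happens to the data of someone who attends fewer.

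- **Progression Plan:** "If individual misses over 75% of all sessions then they may not be included in final analysis, but will remain in the study".
- **Bodyweight Squat Protocol Modifications table**, in the row headed "< 16 visits completed within squat protocol": "Include participant data if at least 8/16 visits are completed during the 8 week squat protocol".

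The Data analysis plan names the tests (for squatting, "analyses of covariance (ANCOVA) will be used at 3 and 6 months after ACLR to test differences in the interlimb ratio"; independent t-tests for T2, strength and gait) and the significance level. The Sample size analysis gives the numbers, for T2 as follows: "A sample size of 30 (15 per group) achieves 81.0% power to detect a group difference" of 2.9 ms with SD 2.7 ms. Neither section defines an intention-to-treat, per-protocol or other analysis set, and neither mentions the attendance rules.

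Under Recruitment & Patient Tracking, group is assigned at enrolment, when the subject ID is issued. The sessions whose attendance is counted follow that assignment.

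**The concern.** There are three linked problems.

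1. The two rules use different cut-offs, and the band between them has no stated status.
2. The wording of the Progression Plan rule is itself ambiguous: it can be read as a prohibition or as permission. If it is permission, participants with 0 to 3 sessions are also decided case by case.
3. Settling the cut-off would not be enough. Either rule, applied to the main comparison, removes participants for something that happens after assignment. The arms receive different programmes (screen feedback and external cues, against no visual feedback and internal cues), so attendance may differ between them. Recovery may also affect attendance.

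If attendance is related to outcome and differs by arm, the difference between those who remain can be biased. With the rules left open, the analysed set could also be settled after outcomes have been seen. With 17 per arm, each exclusion removes about 6% of an arm (1/17).

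**Working it through.** **Where the rules diverge.** This takes 16 planned sessions as the denominator for both rules; the documents give no other total.

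- Progression Plan: 75% of 16 is 12. Missing more than 12 means missing 13 or more, that is, attending 3 or fewer. Attending 4 is missing exactly 75%, which is not over 75%.
- Modifications table: include at 8 or more.

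| Sessions attended | Share missed | Progression Plan | Modifications table |
|---|---|---|---|
| 0–3 | 81.25–100% | may be left out | not admitted |
| 4 | 75.0% | not excluded | not admitted |
| 5 | 68.75% | not excluded | not admitted |
| 6 | 62.5% | not excluded | not admitted |
| 7 | 56.25% | not excluded | not admitted |
| 8–16 | 0–50% | not excluded | included |

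The unsettled band is exactly 4 to 7.

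**How many could fall in it.** No attendance rate is given. If sessions were independent with a common attendance probability (an assumption), the expected number of the 34 in the band would be 0.05 at 80% attendance, 0.9 at 70%, 4.8 at 60% and 13.3 at 50%.

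**The plan's own power figure.** A two-sided two-sample t-test (noncentral t) with difference 2.9 ms, SD 2.7 ms, 15 per arm and alpha 0.05 gives 81.0%, as stated. At the same difference and SD, 14 per arm gives 78.1% and 13 per arm 74.8%. Enrolling 34 leaves room for 34 − 30 = 4 losses, which the plan attributes to attrition without mentioning attendance exclusions.

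**Illustrative bias.** Suppose the lowest-attending fraction p of one arm is dropped, and attendance and outcome are jointly normal with correlation ρ. The arm's mean then shifts by ρ·φ(z_p)/(1 − p) SD, where z_p is the normal quantile at p. The values of p and ρ are assumed; 10–25% of 17 is about 2 to 4 people.

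- p = 0.10, ρ = 0.3: 0.3 × 0.1755/0.90 = 0.058 SD.
- p = 0.25, ρ = 0.5: 0.5 × 0.3178/0.75 = 0.212 SD.
- T2 (× 2.7 ms): 0.16 to 0.57 ms, which is 5–20% of 2.9 ms.
- Knee flexion moment impulse interlimb ratio (ILR), pooled SD √((0.183² + 0.228²)/2) = 0.207: 0.012 to 0.044, which is 4–15% of 0.283. With the arm-specific SDs of 0.183 and 0.228 the range is 0.011 to 0.048 (4–17%).
- 25% dropped from one arm and 10% from the other, same ρ in both: 0.069 SD (ρ = 0.3) to 0.114 SD (ρ = 0.5), or 0.19–0.31 ms, 6–11% of 2.9 ms.
- Same p and ρ in both arms: zero.

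The T2 figures are in milliseconds, as in the sample size section; the Data analysis plan tests percent change in T2.

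**The case against.** The best reply is that this is a gap and not a contradiction. The table says only whom to include, and the Progression Plan only who may be left out. Read literally, both can be true, with 4 to 7 simply not addressed. It is correct that exclusion below 8 is implied and not written. But a threshold of 8 serves no purpose unless those below it are left out, and on either reading nothing in the SAP says what to do with 4 to 7.

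The two rules might also count differently: one refers to all sessions and the other to visits within the 8-week protocol. With 16 planned visits a common denominator is the natural reading, but it is an assumption.

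The practical weight may be small. At 70–80% attendance under independent sessions, fewer than one participant is expected in the band. Clustered non-attendance would change that, and the documents support no particular rate. The bias figures rest wholly on assumed inputs, and the one-arm case is the extreme one. They show scale and predict nothing.

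Finally, the SAP speaks of efficacy, and a minimum-exposure set fixed in advance can be defended as a design choice. That stands for a declared secondary analysis. It does not support two differing, partly discretionary rules with no declared main analysis set.

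**Conclusion.** The concern holds. The rules part at exactly 4 to 7 of 16 sessions, given a common denominator of 16. No analysis set resolves this, and both rules select on attendance after assignment. These points rest on the text and are firm.

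The consequence for the results is conditional. Bias arises only if attendance is related to outcome and the exclusions differ between arms; its direction is unknown and its size may be nil. Under the assumptions shown, a one-arm loss would move the T2 comparison by up to about a fifth of the planned difference, and unequal loss in both arms by about 6–11%. This should be fixed, preferably before outcome data are seen.

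**What to change.** State in the SAP, in words such as: *The main analysis includes all assigned participants with an outcome measurement, in their assigned group, regardless of sessions completed.* Reconcile the Progression Plan and the Modifications table into one attendance definition for analysis, written identically in both places and fixed before outcome data are seen. Use it only for a secondary per-protocol analysis. Report sessions attended by arm. The rules for progressing through the squat levels need not change.

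The direct cost is wording in the protocol and SAP. The fix relies on measuring outcomes in low attenders, which keeping them in the study allows but does not spell out, so this should be stated. Selection through missing outcomes would remain, so missing outcomes should be reported by arm.

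The as-assigned effect may be smaller than the effect among adherers. For example, if 10% of the intervention arm gained nothing, the T2 difference would be 2.9 × 0.9 = 2.61 ms. Power would then be about 72% at 15 per arm, against the stated 81.0%, or 78% if all 17 per arm were measured.

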### **Biofeedback Details:**

\*Progression of each condition requires ≥90% accuracy in 2 consecutive sets of same condition

GRF Only (Weeks 3-4):

-Interlimb threshold begins at 15%; decreases by 1% when 90% accuracy achieved

COP Only (Weeks 5-6):

-Interlimb threshold begins at 10% of shoe length; decreases by 1% when 90% accuracy achieved

GRF, COP or None (Week 7):

-Interlimb GRF and COP thresholds begin at best previously achieved threshold; decreases by 1% when 90% accuracy achieved

-Condition randomly assigned during each set by random number generator (made by [name])

GRF + COP combined (Weeks 8-9):

-Interlimb threshold begins at 5% less than best isolated GRF threshold (min: 85%) and 3% less than best isolated COP threshold (min: 90%)

-Thresholds decrease by 1% when 90% accuracy achieved

GRF, COP, GRF+COP or None (Week 10):

-Interlimb GRF and COP thresholds begin at best previously achieved threshold; decreases by 1% when 90% accuracy achieved

-Condition randomly assigned during each set by random number generator (made by [name])

